Selection of the doses was based on the data of Phase 1 studies in healthy young women and Phase 2 in subjects with uterine fibroids (ASTEROID 1 and 2). In summary, exposure-response analysis of vilaprisan on induced amenorrhea, ovulation inhibition, and on estradiol (E2) levels supported the used of 2 mg and 4 mg doses for the study because

- doses < 2 mg/day can be excluded because they do not achieve the desired maximum effect on induction of amenorrhea and provide insufficient ovarian suppression.

³ 3rd 28 days after start of treatment

- a dose > 2 mg/day may provide additional benefit on endometriosis symptoms which could not be detected in the available data generated in healthy women and subjects with uterine fibroids.
- an intermediate dose is not proposed because there is a considerable overlap in exposure with 2 mg/day and 4 mg/day and thus testing is not expected to provide any additional information.

Justification of original regimen:

PRMs are applied either short-term or in an intermittent treatment regimen to minimize or avoid endometrial changes that may result in episodes of heavy menstrual bleeding (HMB) after cessation of treatment.

Data from ASTEROID 1 show that efficacy of vilaprisan with regard to HMB is achieved rapidly after start of treatment and is maintained during treatment. However, ASTEROID 1 also shows that symptoms return quickly after cessation of treatment, i.e., there is no relevant persistence of treatment effect during the treatment-free interval. This pattern was also observed for other efficacy parameters and is reflected in the assessment of health-related quality of life (HRQoL) which improves during treatment and slightly drops again during the treatment-free phase.

In the absence of data in endometriosis subjects, it is assumed that, like in uterine fibroids, efficacy of long-term (i.e., repeated-intermittent) treatment will be more favorable if treatment phases are longer, because this will result in fewer time with endometriosis-associated pelvic pain (EAPP) and will reduce the slight drops in HRQoL during the treatment-free phases.

Therefore, this study intended to investigate a 6/2 regimen (6 month treatment followed by 2 menstrual bleeding episodes) for long-term, repeated-intermittent treatment with vilaprisan.

Duration of treatment:

Extension of this dose-finding study with a long-term safety study results in a total treatment duration of 12 months was planned. This design was considered justified, because substantial amount of safety data from healthy women and those with uterine fibroids, including repeated treatment courses, was expected to become available. Furthermore, ongoing medical review of study data was conducted to ensure subjects' safety during the study. In subjects with safety findings like suspicious bleeding pattern, increased endometrial thickness or increased liver enzymes treatment was interrupted.

Efficacy / pharmacodynamic assessments:

The endometriosis treatment effect is assessed by investigating the change in the key symptoms of endometriosis (e.g. worst daily pelvic pain, non-menstrual pelvic pain, dysmenorrhea, dyspareunia). In the absence of biomarkers, and considering the inherently subjective nature of the symptoms, this can only be rated appropriately by the subjects themselves, using Patient-Reported Outcomes (PROs) which substantiates the clinical investigation.

Ultrasound assessment of endometriosis lesions, hormone levels, and bleeding will be determined as pharmacodynamic (PD) parameters.

Safety monitoring:

Safety parameters were regularly and closely monitored throughout the study (eg, questioning for adverse events (AEs), measurement of laboratory values, vital signs, endometrial safety monitoring, endometrial thickness, abnormal menstrual bleeding, and size of follicle like structures comprising follicles and functional ovarian cysts). A comprehensive evaluation for adrenal tumors and a skin examination are implemented with Protocol Amendment no. 7.

Endometrial monitoring

A careful endometrial safety monitoring assessment was applied in this study from the beginning including regular ultrasound investigations, observation of bleeding patterns, and endometrial biopsies at defined time points. Clear decision trees are outlined as to when to perform an additional unscheduled endometrial biopsy in case of endometrial thickening and/or on the clinical management of endometrial thickening/HMB/ suspicious bleeding pattern (see Section 9.6.3.1). Reliable diagnosis of any findings in the endometrial biopsies is ensured through the involvement of a panel of highly experienced and well renowned expert pathologists who will assess every biopsy sample taken from study participants.

With Protocol Amendment no. 7, additional requirements for endometrial safety monitoring are outlined for subjects who took at least one dose of study medication vilaprisan, see section 9.6.3.1.2.

Liver monitoring

A liver-related safety signal was observed with some progesterone receptor modulator (PRM) compounds which display differences in molecular structure compared to vilaprisan.

Monthly monitoring of liver parameters under treatment was introduced with an earlier version of this protocol. With this protocol amendment, subjects will receive one further laboratory examinations, including liver parameters.

Adrenal monitoring

A comprehensive adrenal screening program is implemented with Protocol Amendment no. 7. This program is described in more detail in Section 9.6.3.8. It encompasses adrenal imaging, as well as laboratory tests aimed at identifying overproduction of adrenal cortical hormones in the context of tumors of the adrenals. Tumors of the adrenal glands (cortical or medullary in origin, benign as well as malignant) are known to occur in a certain frequency in the general population, independent of an exposure to the study drug vilaprisan (5). For adrenal tumors detected by the screening program in this study, a causal relationship to vilaprisan can therefore not be automatically assumed.

Skin monitoring

In the above-mentioned carcinogenicity study performed in mice, skin sarcomas were found at a dose representing about 100 and 50 times the human therapeutic doses of 2 mg and 4 mg, respectively. The tumors were derived from various cell lineages and were seen at various anatomical locations. The cause and the relevance of the skin tumors in mice is unclear but based on the high exposure at which these tumors were found, the relevance for humans treated at the intended therapeutic dose is regarded as limited.

Nevertheless, all study participants who took at least one dose of vilaprisan will be asked to undergo a thorough skin examination by a dermatology expert in order to demonstrate skin safety of repeated intermittent treatment with vilaprisan.

Assessment of effects on bone mineral density

Selective PRMs such as vilaprisan induce a degree of ovulation suppression, accompanied by a moderate decrease in endogenous estradiol levels. BMD is assessed in this study using dual-energy X-ray absorptiometry (DEXA).

BMD measurement of the spine (lumbar anterior posterior, L1-L4) and hip/femoral neck is performed using the same type of device for all measurements of any subject in this study.

DEXA is associated with radiation exposure but the total exposure per examination is only approximately 0.005 mSV corresponding to 3 to 4 hours of natural background radiation. No contrast agent is needed for this examination.

All subjects who received vilaprisan treatment should have an off-treatment DEXA scan performed at a timepoint at least 22 weeks after last intake of vilaprisan, to document absence of bone loss or adequate recovery.

Effects related to study conduct

In addition to drug-related side effects, symptoms caused by the study conduct (eg, due to blood sampling, endometrial biopsy) are possible. However, possible risks are regarded as acceptable because the planned methods are used routinely in clinical studies, clinical and/or gynecological practice.

Pregnancy

Due to the mode of action of the tested study drug, information on teratogenic potential of vilaprisan is limited. Therefore clear instructions with regards to contraceptive methods and regular pregnancy testing have been implemented in order to avoid exposure to the study drug during pregnancy.

End of study

The end of the study as a whole will be reached as soon as the last visit of the last subject has been reached in all centers in all participating countries (EU and non-EU).

Primary completion

The primary completion event for this study is last patient last visit (LPLV).

The primary completion date for this study according to the Food and Drug Administration Amendment Act is specified in a separate document (not part of this study protocol).

6. Study population

No longer valid, since no new subjects will be enrolled in this study with the implementation of Protocol Amendment no. 7.

Originally the study population had to fulfill the following criteria:

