- Endometrial biopsy (in case a valid post-treatment biopsy is not already available)
- Laboratory (blood sampling)
- DEXA scan measurement for bone mineral density
- Collection of unused study drug and empty drug packs/drug accountability, if applicable
- Collection of eDiary device
- Deactivation of the subject on the tablet computer without selecting a particular visit

At the second scheduled visit (“Safety Result Reporting Visit”), the investigator is asked to communicate the results from the safety evaluations to the subject. This can be done as a telephone visit.

Details regarding the safety evaluation procedures and algorithms for identified abnormalities can be found in the respective sections of Protocol Amendment no. 7. Test results (e.g., hormone, liver, physical examination) may be abnormal but still below the thresholds to trigger outside evaluation in the context of the study. In these cases subjects should at least be counseled about medical follow up according to local practice.

Before a subject is deemed lost to follow up, the investigator or designee must make every effort to regain contact with the subject (where possible, 3 telephone calls and, if necessary, a certified letter to the subject's last known mailing address or local equivalent methods). These contact attempts should be documented in the subject's source documents.

For subjects who received placebo treatment prior to the temporary pause, no further procedures are required except for the collection of eDiary device and deactivation of the subject on the tablet computer.

Table of contents

Cover page of the integrated protocol.....	1
1. Title page.....	2
Signature of the sponsor's medically responsible person	3
Signature of the investigator	4
2. Synopsis.....	5
Protocol Amendment Summary of Changes Table.....	10
Table of contents.....	13
Table of tables.....	16
Table of figures	16
List of abbreviations.....	17
Definitions of terms	20
3. Introduction	21
4. Study objectives	24
5. Study design.....	26
6. Study population	32
6.1 Eligibility	32
6.2 Inclusion criteria	32
6.3 Exclusion criteria	33
6.4 Justification of selection criteria	36
6.5 Withdrawal of subjects from study	36
6.5.1 Withdrawal	36
6.5.2 Replacement	37
6.6 Subject identification	37
7. Treatments	38
7.1 Treatments to be administered	38
7.1.1 Start and end of study treatment	38
7.1.2 Missed intake of study drug	39
7.1.3 Rescue pain medication	39
7.1.4 Other pain medication	40
7.1.5 Diet	40

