9.1 Tabular schedule of evaluations

No longer valid, since with the implementation of Protocol Amendment no.7 no subjects will be recruited and none of the enrolled subjects will receive further study drug treatment. All subjects who were randomized and started treatment with vilaprisan before the temporary pause will be asked to have the “Safety Closeout visit” with a comprehensive safety evaluation (with particular focus on endometrial, adrenal and skin safety) which is implemented with Protocol Amendment no. 7. This also applies to subjects who have discontinued the study before or during the temporary pause, provided they have taken at least one dose of study medication vilaprisan. The second scheduled visit, the “Safety Result Reporting visit” can be done as a telephone visit.

This “Safety Closeout visit” should be performed in all subjects as soon as possible after implementation of Protocol Amendment no.7. The following procedures are to be done:

Table 9–1: Schedule of procedures

Visit	Safety Closeout Visit ⁷	Safety Result Reporting visit (can be Telephone visit)
Timing	After approval of Protocol Amendment no. 7	Once all safety results are available
Informed consent	X	
Concomitant medications	→	→
AE assessments	→	→
Adrenal disorder signs and symptoms incl. vital signs ⁸	X	
MRI of adrenal glands ⁹	X	
DEXA scan for bone mineral density ¹⁰	X	
Dispense saliva test tubes	X	
Collect saliva test tubes ¹¹	X	
Referral to dermatology expert	X	
Physical examination	X	
Body weight	X	
Gynecological/breast exam ¹²	X	
Urine pregnancy test	X	
Cervical cytology ¹³	X	
Ultrasound examination ¹⁴	X	
Endometrial biopsy ¹⁵	X	
Laboratory (blood) ^{16, 17}	X	
Collection of unused study drug and empty drug packs/drug accountability	X if applicable	
Collection of eDiary device and review of bleeding data and assessment of any abnormal bleeding pattern	X if applicable	
Deactivation of subject on tablet computer without selecting a particular visit	X	
Communication of results from safety evaluations to the subject		X

⁷ In most cases the procedures scheduled for this visit will not take place on the same day

⁸ Blood pressure in triplicates and heart rate after 5 minutes of rest in a sitting position

⁹ Negative pregnancy test is a prerequisite

¹⁰ Negative pregnancy test is a prerequisite

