¹¹ Saliva tests should be performed as soon as possible after this visit to allow for a repeat in case of unevaluable results or for review by one of the adrenal experts in case of abnormal results. The two samples should be returned to the study site preferably on the day after collection of the last sample.

¹² Only to be performed if subject did not have these performed with normal result after end of treatment

¹³ Only to be performed if subject did not have this performed with normal or clinically insignificant result after end of treatment, negative pregnancy test is a prerequisite; for subjects with menstrual cycles the endometrial biopsy should be taken between Day 7 to 15 (inclusive) of a menstrual cycle

¹⁴ The ultrasound must be done before the biopsy

¹⁵ Only to be performed in subjects who did not have a post-treatment endometrial biopsy (defined as biopsy taken at the earliest 7 days before last study drug intake) with a normal result. This is defined as diagnosis of safety read and of all 3 individual components of the multiread to be "benign endometrium" in Part II of the evaluation form. In addition, the majority diagnosis needs to be "PAEC no" in Part IV of the evaluation form. Furthermore, an endometrial biopsy may also be triggered by results of ultrasound examination or bleeding data (see Section 9.6.3.1). The biopsy CRF page needs to be completed for all subjects, including cases where according to protocol no biopsy is required.

¹⁶ The blood should be withdrawn under fasting conditions between 6 am and 10 am.

¹⁷ In subjects who take biotin, the last dose of biotin should be at least 72 hours prior to hormone testing.

Subjects who received treatment with placebo prior to the temporary pause will be asked to return the eDiary device. Thereafter, subjects will be deactivated on the tablet computer.

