9.6.1.6 Adverse events of special safety interest

The investigators will assess all AEs to determine if they are AEs of special interest (AESIs) and document this in the eCRF. Adverse events from the following areas should be considered for reporting as AESI according to the following guidance:

- Liver disorders:
 - For all cases which qualified for “close observation” before implementation of Protocol Amendment no. 7 and/or qualify for “ruling out of alternative cause” after implementation of Protocol Amendment no. 7 (see Section 9.6.3.9), the underlying event should be recorded as AESI in the AE eCRF.
- Endometrial disorders:
 - Endometrial hyperplasia (all subcategories according to WHO 2014 [and WHO 1994] classification), for monitoring and FUP see Section 9.6.3.1

- Endometrial thickening >18 mm: If endometrial thickness (double layer) >18 mm is detected after the start of treatment, the subject should undergo immediate evaluation by endometrial biopsy as described in Section [9.6.3.1.4](#).
- Skin disorders:
 - Any dermatology expert's diagnosis of a pre-cancerous or malignant skin lesion, including cutaneous sarcoma confirmed by biopsy diagnosis, qualify as an AESI. Malignant skin lesions should be reported as an SAE to ensure timely reporting to regulatory agencies.
- Adrenal disorders
 - A robust adrenal safety monitoring program has been implemented in all ongoing vilaprisan studies, including MRI of the adrenal glands, laboratory parameters, and evaluation of signs and symptoms indicative of adrenal disorder. A systematic approach of assessment and evaluation of adrenal gland findings will be applied as described in Section [9.6.3.8](#). Any adrenal abnormality assessed as relevant by either the adrenal gland expert or the local specialist will need to be documented as an AESI and to be reported to the sponsor's pharmacovigilance department following the same standard process (reporting timelines, AE CRF and AE complementary pages) as serious AE. Tumors of the adrenal glands (diagnosed by the MRI central read, the adrenal gland expert or the local specialist) should in addition be reported as SAEs to ensure timely reporting to regulatory agencies.
- Relevant loss of BMD:

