9.6.3.3 Laboratory evaluations

Only blood and urine samples analyzed at the central laboratory will be considered for analysis. The name and address for the central laboratory service provider can be found in the documentation supplied by the vendor.

In the event of implausible results, the laboratory may measure additional parameters to assess the quality of the sample (e.g. clotted or hemolyzed) and to verify the results. The results from such additional analyses may neither be included in the clinical database of this study nor evaluated further. If the results are relevant, the investigator will be informed to determine follow-up activities outside of this protocol.

The following parameters will be assessed at the safety closeout visit in subjects who remained in the study during the temporary pause:

Hematology: leukocytes, erythrocytes, hemoglobin (Hb), hematocrit, mean corpuscular volume (MCV), mean corpuscular hemoglobin (MCH), platelets, neutrophils, eosinophils, basophils, lymphocytes, and monocytes.

Blood test for hepatitis A, B, and C (only in case of elevated liver enzymes requiring further follow up): anti-HAV Immunoglobulin M (IgM), HBs-Ag, anti-HCV, and HCV-mRNA (assessed only in cases with a positive result for anti-HCV).

Serum chemistry: creatinine, chloride, potassium, sodium, calcium, total protein, albumin, total cholesterol, high density lipoprotein (HDL) cholesterol, low density lipoprotein (LDL) cholesterol, triglycerides, ALT, AST, AP, gamma-glutamyl transpeptidase (γ -GT), and total bilirubin. (in case the result is $> 2 \times \text{ULN}$, conjugated and unconjugated bilirubin will be determined).

See Section 9.6.1.6 for procedure in case of elevated liver parameters.

Biochemistry: glycosylated hemoglobin (HbA1c) and ferritin.

Additional parameters²⁰: hormones (follicle-stimulating hormone [FSH], luteinizing hormone [LH], estradiol [E2], progesterone [P], prolactin, and thyroid-stimulating hormone [TSH]), bone markers (bone-specific alkaline phosphatase, osteocalcin, and collagen type 1 cross-linked C-telopeptide [CTX]), and **vitamin D** (serum 25-hydroxyvitamin D).

In case of elevated liver enzymes requiring investigation of alternative cause the following parameters will have to be determined (in earlier CSP versions this was summarized in a particular section “close observation”).

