Serum chemistry panel (see above), A1AT level, conjugated bilirubin, ceruloplasmin, cholinesterase, CK, ferritin, full blood count (incl. eosinophilia), hemoglobin, INR, iron, LDH, platelets, PT, total iron binding capacity (TIBC), testing to rule out Hepatitis A-, Hepatitis B-, Hepatitis C-, potentially also Hepatitis D- Hepatitis E-, Cytomegalo-, Epstein-Barr-, and Herpes simplex virus infection, brucellosis, leptospirosis, and toxoplasmosis, ANA/ANCA screening test with further tests depending on result and IgA, IgG, and IgM.

²⁰ Blood samples should be taken at least 72 hours after the intake of high doses of biotin, since the laboratory results of ferritin, TSH, FSH, LH, estradiol, prolactin, progesterone, cortisol, ACTH and β -CTx may be affected, if the subject had a biotin intake at a concentration higher than 5 mg per day which occurred less than 72 hours before the sample is taken.

Parameters measured for adrenal monitoring:

- serum cortisol (to be measured between 6 am and 10 am)
 - ACTH will be assessed from the same sampling if the cortisol measurement yields an abnormal value.
- late night salivary cortisol (to be obtained between 11 PM and midnight)
- serum dehydroepiandrosterone sulfate (DHEA-S)
 - the age-specific DHEA-S ratio (derived by dividing the patient's DHEA-S value by the lower limit of the age-specific reference range) will be calculated. In case of an abnormal DHEA-S ratio ACTH will be assessed from the sample taken for serum cortisol measurement
- serum total testosterone (tT)
- serum glucose measurement under fasting conditions
- serum potassium.

The following parameters will be assessed at the safety closeout visit in subjects who have discontinued the study before or during the temporary pause:

- estradiol
- vitamin D (serum 25-hydroxyvitamin D)
- **Parameters measured for adrenal monitoring:**
 - serum cortisol (to be measured between 6 am and 10 am)
 - ACTH will be assessed from the same sample if the cortisol measurement yields an abnormal value.
 - late night salivary cortisol (to be obtained between 11 PM and midnight)
 - serum dehydroepiandrosterone sulfate (DHEA-S)
 - the age-specific DHEA-S ratio (derived by dividing the patient's DHEA-S value by the lower limit of the age-specific reference range) will be calculated. In case of an abnormal DHEA-S ratio ACTH will be assessed from the sample taken for serum cortisol measurement.
 - serum total testosterone (tT)

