9.6.3.9 Liver monitoring

In the past, investigators, subjects and their family members were instructed to be alert for nonspecific symptoms which may be associated with liver dysfunction, see [Section 9.6.3.9.1](#). In addition, the liver inquiry had to be completed at regular intervals. Based on the long interval between implementation of Protocol Amendment no. 7 and last intake of study drug this is no longer needed on a routine basis.

Investigation of potential alternative causes (which replaces the close observation procedures applied before this protocol amendment) however has to be initiated and recorded in the dedicated liver case report form if at least one of the options below applies:

- GPT/ALT or GOT/AST value increases to $> 3 \times \text{ULN}$
or
- GPT/ALT or GOT/AST value 2-fold increases above the lowest baseline value for subjects with elevated values before drug exposure
or
- AP (alkaline phosphatase) value increases to $> 2 \times \text{ULN}$ and irrespective of the level of transaminase (GPT/ALT or GOT/AST) values
 - in cases with baseline showing normal AP
 - in cases of at least 2 times the baseline values if slightly above the upper limit of normal at baseline

In those cases, a search for alternative explanations should be performed including:

- Repeating a serum chemistry panel (including liver parameters and bilirubin).
- Obtaining a more detailed history of the symptoms and prior or concurrent diseases.
- Obtaining a history of concomitant drug use (including nonprescription medications and herbal and dietary supplement preparations), alcohol use, recreational drug use, and special diets.
- Ruling out acute viral hepatitis; autoimmune or alcoholic hepatitis; non-alcoholic steatohepatitis (NASH); hypoxic/ischemic hepatopathy; and biliary tract disease. This may require performing additional procedures, e.g. ultrasound examinations.
- Obtaining a history of exposure to environmental chemical agents.

- Obtaining additional tests to evaluate liver function as appropriate, (eg, international normalized ratio [INR], total bilirubin measurements).
- Referral for a liver ultrasound.

Any of these additional findings is to be recorded on the corresponding eCRF pages.

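### Does Section 5 promise closeout liver tests that Section 9.6.3.3 does not schedule for vilaprisan-treated subjects who left the study?

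*Protocol*

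**What the plan says.** Section 5 of the protocol, in the Liver monitoring paragraph of its design justification, recalls that monthly liver testing was introduced under an earlier protocol version. It then says that with the amendment "subjects will receive one further laboratory examinations, including liver parameters".

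Section 9.1 extends the closeout visit beyond those still in the study: "This also applies to subjects who have discontinued the study before or during the temporary pause", on condition that they took vilaprisan. The short summary for sites says the same, and adds that placebo subjects have no further procedures beyond returning the diary device and being deactivated on the tablet.

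Section 9.6.3.3 gives two lists. The first opens "The following parameters will be assessed at the safety closeout visit in subjects who remained in the study during the temporary pause" and includes a serum chemistry block with ALT, AST, AP, gamma-GT and total bilirubin. The second opens "The following parameters will be assessed at the safety closeout visit in subjects who have discontinued the study before or during the temporary pause" and contains estradiol, vitamin D and the adrenal parameters.

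Section 9.6.3.9 says that a search for alternative causes "has to be initiated and recorded in the dedicated liver case report form if at least one of the options below applies"; the options are rises in ALT, AST or AP. Section 9.6.1.6 adds that for cases meeting those criteria "the underlying event should be recorded as AESI in the AE eCRF".

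**The concern.** Read on its own, the Section 5 sentence covers everyone who comes to closeout, and that includes vilaprisan-treated subjects who had already left. Section 9.6.3.3 then schedules no liver test for them. Two other places could strengthen the impression that liver results are expected for all. The short summary for sites says "Test results (e.g., hormone, liver, physical examination) may be abnormal but still below the thresholds to trigger outside evaluation" without separating the groups. The blood laboratory row of Table 9-1 is not split either; its two footnotes deal with fasting ("The blood should be withdrawn under fasting conditions between 6 am and 10 am") and biotin, although footnotes on other rows do restrict procedures to subsets.

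If the texts led sites in different directions, some discontinued subjects would have closeout liver values and others would not. Without a value, neither the work-up in Section 9.6.3.9 nor the part of the liver AESI in Section 9.6.1.6 that depends on it could start from a scheduled closeout sample. Liver safety has been a regulatory concern for this drug class, as the history of Amendments 2 and 3 shows, so the question is a fair one.

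**Working it through.** No sample size, power or error rate enters, so the check sets the texts side by side and counts.

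**1. What each place specifies for closeout**

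| Place | Subjects named | Liver parameters named |
|---|---|---|
| Section 5, Liver monitoring | Subjects, no qualifier | Mentioned generically, no analyte |
| Table 9-1, blood row | All closeout subjects | No analyte of any kind |
| Short summary for sites | Those with abnormal results | Liver given as one example |
| 9.6.3.3, first list | Remained during the pause | ALT, AST, AP, gamma-GT, total bilirubin: 5 |
| 9.6.3.3, second list | Discontinued before or during the pause | 0 |
| 9.6.3.9 | No sampling group stated | Acts on ALT, AST, AP; schedules no sample |

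**2. Count in the second list.** Estradiol, 25-hydroxyvitamin D, serum cortisol, late-night salivary cortisol, DHEA-S, total testosterone, fasting glucose and potassium make 8, with ACTH added only if cortisol or the DHEA-S ratio is abnormal. Overlap with the 5 routine liver parameters: 0. The additional liver work-up panel in 9.6.3.3 does not fill the gap, because it applies only once enzymes are already known to be raised. The factual core of the concern is therefore correct.

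**3. Is the second list a slip or a rule?** It has its own heading and its own population. It also omits haematology, lipids, HbA1c, ferritin, the bone markers and all the first list's additional hormones except estradiol. A list that drops whole blocks and keeps estradiol, vitamin D and the adrenal set looks like a deliberately reduced panel. It matches the focus given in the short summary for sites, which is endometrium, adrenals, bone and skin. Section 9.6.3.9 also withdraws the routine liver symptom inquiry because so much time has passed since the last dose.

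**4. Can the Section 5 sentence be taken literally?** No. Unqualified, it would also cover placebo subjects, who have no closeout laboratory at all. Some qualifier has to be supplied on any reading. The neighbouring skin and bone paragraphs state their populations; the liver paragraph does not.

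**5. Would a site be misled?** Nobody can order tests from Section 5, which names no analyte and no visit. Table 9-1 says only that blood is drawn, which is true of both groups. The subset footnotes on other rows govern whether a procedure is done at all, so the lack of one on the blood row carries little weight. The summary's mention of liver is an example in a sentence about counselling, and its paragraph refers readers to the detailed sections.

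**6. Does the possible harm come from the mismatch?** All 3 triggers in 9.6.3.9 need ALT, AST or AP, so 0 of 3 can be judged from the second list. But that follows from the 9.6.3.3 panel alone. Adding a scope phrase to Section 5 would leave the count at 0 of 3. The count describes a testing choice, not the inconsistency.

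**7. How many subjects?** Section 3 gives 8 enrolled of 315 planned: 8/315 = 2.5%. Assuming all 8 were randomized 1:1:1 and treated, about 8 × 2/3 = 5.3 would be on vilaprisan. Those who also discontinued are a subset of these, anywhere from zero upward; the documents give no figure.

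**8. What analysis depends on it?** Protocol 10.1 and SAP 4.1 limit the output to listings, and SAP 6.4 lists safety data as recorded. A test that was not scheduled simply does not appear.

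**The case for a change.** The strongest case for acting is that the protocol demands strict adherence (Section 13.3) and has no rule on which section prevails, so two statements that differ in scope should not coexist. The closeout is also meant to assure subjects that they leave without a worrying finding. With the structured liver inquiry dropped as well, discontinued subjects have no scheduled liver-specific assessment at closeout, although Section 5 reads as if they do. The repair would cost a few words.

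Part of this stands. The wording does disagree, no rationale for the split is given, and the passages should be reconciled so that they name the same subjects. The rest does not lead to a change in the plan. If the sponsor confirms the split, the repair adds a phrase to an overview and changes nothing that is done or reported. If the sponsor intended liver tests for everyone, the panel itself would change, but that is a clinical decision the documents do not settle and this review should not make. In either case, earlier liver values, adverse event reports and unscheduled visits (Section 9.2.1) remain available for these subjects. The AESI limb covering cases identified before Amendment 7 needs no closeout sample.

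**Conclusion.** This is a drafting slip: a one-line overview in Section 5 does not carry the split that Section 9.6.3.3 makes in detail. The two passages should be reconciled as housekeeping, with the choice of who is tested left to the sponsor. No change to conduct or analysis follows. The difference is 5 routine liver parameters against 0, in at most a subset of 8 enrolled subjects and possibly in none, and it affects no estimate, test or summary.

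The conclusion rests on two assumptions. The first is that the two panels in Section 9.6.3.3 are intended, which their separate headings and the breadth of what the second omits support but do not prove. The second is that sites order blood tests from the section that names the analytes. If the first were wrong, the issue would be a clinical testing decision for the sponsor; the listings-only analysis would still be unaffected.
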